3.4 Withdrawal of Subjects

Subjects may withdraw from the study at any time or be withdrawn from the study at the discretion of the investigator should any untoward effects occur. In addition, a subject may be withdrawn by the investigator or the sponsor if she deviated from the protocol or for other safety reasons.

Subjects withdrawing from the study will not be replaced, regardless of the reason for discontinuation. All reasonable efforts should be made to contact the subject if she decides to discontinue study treatment.

The procedures noted in the Schedule of Assessments ([Table 3](#)) should be performed for the Early Termination Visit, whenever it occurs. A subject will be considered to have completed the study after completing the Test of Cure Visit (Visit 3). If a subject is discontinued at any time after entering the study, the investigator will make every effort to see the subject and complete the early discontinuation assessments as shown in Schedule of Assessments ([Table 3](#)) and [Section 5.4](#).

A termination electronic case report form (eCRF) page should be included for each subject who receives study medication, whether or not the subject completes the study. The reason for any early discontinuation should be indicated on the form. The primary reason for a subject withdrawing prematurely should be selected from the list provided in [Section 6.2](#).

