5.3 Test of Cure Visit (Visit 3)

The Test of Cure Visit (Visit 3) will occur 21 to 30 days after Visit 1. This is the last visit of the study. The following will be completed:

- Perform physical examination.
- Obtain vital signs after sitting for 5 – 10 minutes ([Section 4.5](#)).
- Measure weight.
- Perform urine pregnancy test.
- Perform pelvic examination including vaginal wall inspection (a naked eye inspection), examination of the cervix, and Investigator's (or designee's) assessment of local site reactions.
- Record subject-assessed local site reactions (e.g., itching, burning/stinging, localized pain).
- Collect a swab sample for central laboratory Nugent's analysis for BV via Gram stain.
- Determine clinical cure of BV by assessing the subject for presence of the following three Amsel's criteria:
 - Resolution of the abnormal vaginal discharge characteristic of BV to a normal physiological discharge; AND
 - Negative "whiff test" after addition of a drop of 10% KOH to vaginal discharge; AND
 - Presence of clue cells at <20% of the total epithelial cells on microscopic examination of the saline wet mount.
- Determine if vaginal pH is <4.7, which is part of the assessment of therapeutic cure (defined as clinical cure, vaginal pH <4.7 and bacteriological cure).
- Record concomitant medications taken since the prior visit along with the indications for the medications.
- Assess and record AEs.

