8.1.3 Reporting Procedures and Requirements for Adverse Events

8.1.3.1 Study Reporting Period for Adverse Events

At every visit or contact, study staff will ask each participant how she felt since her last visit and indirectly ask if she has experienced any AEs.

The reporting period for AEs is the period immediately following the signing of the ICF through 30 days after last use of study product.

For the purposes of study analysis, if a non-serious AE has not resolved at the end of the study-reporting period it will be reported as still ongoing in the EDC system. However, the investigator must make every reasonable effort to follow the event to resolution or stabilization and report to [REDACTED].

SAEs must be followed until resolution. Resolution of an SAE is defined as the return to baseline status or stabilization of the condition with the expectation that it will remain chronic.

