3.4 Analysis Populations

All Screened Population: all subjects who signed Consent Form and screened at the study sites.

Intent-to-Treat (ITT) Population: All randomized subjects.

Safety Population: All randomized subjects who received at least 1 dose of study drug. If the drug accountability is unknown (e.g., due to being lost to follow-up after being randomized) then subjects will be assumed to have taken study drug and included in the safety population. Subjects reporting 0 doses will be excluded.

Modified Intent-to-Treat (mITT) Population: a subset of the Safety Population who also met all 4 Amsel's criteria at baseline, but excluding those who subsequently demonstrate a positive or indeterminate test result for other concomitant vaginal or cervical infections at baseline (e.g. *C. trachomatis*, *N. gonorrhoeae*) which may interfere with the efficacy assessment for BV, or who have a baseline Nugent's score < 4. If baseline STI value is missing, use the Post-Treatment Assessment Visit infection test result. Subjects without a Nugent's score at baseline will be excluded from the mITT population.

Per Protocol (PP) Population: All mITT subjects except for those who had at least one of the protocol deviations listed below. If lack of efficacy (LOE) is the discontinuation reason and the subject took at least 3 doses, then the subject will be included in PP as a treatment failure and then the 6 protocol deviations below will not exclude those subjects:

1. Used topical or systemic antimicrobial drugs after randomization, this includes the following drug classes: antimycotics, antibacterials, antiprotozoals, gynecological anti-infectives, antiseptics and antifungals.
2. Used non-study vaginal products during the study
3. Did not start treatment within 2 days of randomization
4. Took less than 5 doses of study drug
5. Test of cure visit (V3) was not in the Study Day 22 – 31 window, i.e., Visit 3 was not 21 – 30 days after randomization
6. Test of cure visit (V3) not done

Other important violations that represent material non-compliance with study drug or protocol that would impact the primary and secondary efficacy endpoints will be reviewed prior to database lock (i.e., before unblinding). These will be documented in the Evaluability Memo which will be included in the clinical study report.

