3.5.6 Prior Medications

All medications taken by the subject for one month prior to randomization (pre-study) and during the study will be recorded on the prior and concomitant medication CRF page. Prior medications are medications that were taken up to one month before randomization, and concomitant medications are medications taken on or after the subject was randomized.

Medications will be coded to the therapeutic drug classes and generic drug names by using the World Health Organization (WHO) Drug Dictionary, March 2016 version. The codings will be reviewed by qualified medical personnel, and then summarized by treatment group and for all subjects with the number and percentage of ITT subjects who had prior medications that were coded to each generic drug name and therapeutic drug class, as well as the number and percentage of subjects who had at least one prior medication. Subjects reporting more than one drug in each drug class/generic name are only counted once to that drug class/generic name.

Prior medications will be also be summarized by the descending order of frequencies (total number of ITT subjects) for drug class (i.e., no generic drug names provided).

For the purpose of assessing prior and concomitant medications, the following rules will be used for partial or missing medication start and stop dates.

D=Day, Y=Year, M=Month

Parameter	Missing	Comments	Imputation
Start date	D only	M and Y same as M and Y of first dose of study drug	Date of first dose of study drug
		M and/or Y not same as date of first dose of study drug	First day of month
	M and D	Y same as Y of first dose of study drug	Date of first dose of study drug
		Y not same as Y of first dose of study drug	Use Jan 01 of Y
	M, D, and Y	None - date completely missing	Day prior to date of first dose of study drug

Stop date	D only	M and Y same as M and Y of last dose of study drug	Date of last dose of study drug
		M and/or Y not same as date of last dose of study drug	Last day of month
	M and D	Y same as Y of last dose of study drug	Date of last dose of study drug
		Y not same as Y of last dose of study drug	Use Dec 31 of Y
	M, D, and Y	None - date completely missing and NOT ongoing	Date of last dose of study drug

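### Per Protocol deviation 1 does not stop at the Visit 3 exam, so a completer who fails and then has an antimicrobial recorded is dropped from the equivalence population because she failed

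*SAP*

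**What the plan says.** SAP 3.4 lists six deviations that remove an mITT subject from PP. The first is "Used topical or systemic antimicrobial drugs after randomization". It starts at randomization and names no closing date, visit or exam. The second reads "Used non-study vaginal products during the study", which at least refers to the study period.

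The one exemption from all six begins "If lack of efficacy (LOE) is the discontinuation reason and the subject took at least 3 doses". It therefore needs a discontinuation. Protocol 3.4 treats any woman who attends Visit 3 as a completer, cured or not: "A subject will be considered to have completed the study after completing the Test of Cure Visit (Visit 3").

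On data capture, SAP 3.5.6 says "concomitant medications are medications taken on or after the subject was randomized", again with no upper limit in the definition, although the preceding sentence speaks of medications recorded during the study. Protocol 5.3 instructs sites at Visit 3 to "Record concomitant medications taken since the prior visit along with the indications for the medications" and says of Visit 3 "This is the last visit of the study". Protocol 8.1.3.1 runs adverse event reporting "through 30 days after last use of study product".

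SAP 3.7 uses PP for the test-reference comparison and mITT for the comparisons with placebo.

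**The concern.** Visit 3 is where failure is established and also where medications are recorded. An antimicrobial started at or after that exam cannot alter its result, yet under the literal rule it makes the woman a deviator. A woman who has failed has a BV-related reason to receive such a drug; a cured woman does not. Membership of the primary equivalence population can thus depend on the endpoint itself.

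The result also sits oddly with the exemption. A failure who leaves early for lack of efficacy after three doses stays in PP. A failure who finishes the trial with a valid Visit 3 outcome can be dropped.

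At stake are the observed PP cure rates, the PP sample size and the test-reference difference on which equivalence is decided.

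**Working it through.** **The plan's own figure.** Inputs from SAP 2.5: 36% active, 20% placebo, 12.4% not in mITT, 90% power; two-sided 5% from SAP 3.1.2.

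- Without continuity correction: (1.960·√(2·0.28·0.72) + 1.282·√(0.36·0.64 + 0.20·0.80))² / 0.16² gives 164 per arm.
- With continuity correction: 176 per arm.
- 176 / 0.876 gives 201 per arm, and 3 × 201 = 603, as stated.
- At 176 per arm and 36% v 40%, the SAP's equivalence interval has 90.8% power by normal approximation, consistent with the stated target.

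None of this depends on deviation 1.

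**Assumptions for the effect of the rule.** The planned 738 give 246 per arm, and 246 × 0.876 ≈ 215 in mITT. PP will be smaller; I assume 200 per arm before this rule acts. Let f be the share of Visit 3 failures removed. The documents give no value, so it is shown as a range.

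For a true cure rate p:

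- expected PP cure rate = p / (1 − f(1 − p))
- expected PP size = n(1 − f(1 − p))

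**Worked example, 36% v 40%, f = 0.5.** Test: 0.36/0.68 = 52.9%, n = 136. Reference: 0.40/0.70 = 57.1%, n = 140. The difference barely moves (−0.040 to −0.042), but the standard error rises from √(0.2304/200 + 0.24/200) = 0.0485 to √(0.529·0.471/136 + 0.571·0.429/140) = 0.0598. The cost is power.

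**Simulation.** Binomial outcomes, failures removed with probability f, then the SAP 3.7.1 90% interval with Yates' correction against ±0.20. Entries are the probability of concluding equivalence, with f equal in both arms.

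| True rates (test v reference) | f = 0 | 0.25 | 0.5 | 0.75 | 0.9 |
|---|---|---|---|---|---|
| 36% v 36% | 98.6% | 95% | 88% | 82% | 92% |
| 36% v 40% | 94% | 88% | 80% | 78% | 93% |
| 16% v 36% (at margin) | 3.9% | 1.1% | 0.3% | 0.4% | 4.5% |
| 20% v 40% (at margin) | 3.9% | 1.5% | 0.8% | 1.4% | 13% |
| 33% v 53% (at margin) | 3.7% | 3.2% | 4.3% | 16% | 66% |

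In the last three rows the products differ by exactly the margin, so the entry is the false-equivalence rate. The 53% is the label's once-daily rate (98/185, Protocol Appendix 1). That row passes 5% at about f = 0.6 (6%).

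**Unequal f (0.25 test, 0.10 reference).**

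- 33% v 53%: 0.33/0.8325 = 39.6% and 0.53/0.953 = 55.6%. The difference shrinks to −0.160 and false equivalence is 16%.
- 20% v 40%: 0.20/0.80 = 25.0% and 0.40/0.94 = 42.6%. The difference shrinks to −0.176 and false equivalence is 10%.

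Imbalance the other way hurts the sponsor. At 36% v 40% with 215 per arm, f = 0.25 test and 0.50 reference gives a PP difference of −0.143 and about 24% power.

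**Partial dates.** SAP 3.5.6 imputes a start date with the day missing to the first-dose date if it falls in the first-dose month, otherwise to the first of its month, and a wholly missing start to the day before first dose. Any of these can move a drug started after Visit 3 to before it, so a date cut-off alone would not fully close the gap.

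**The case against.** The best defence is that the documents imply a limit. SAP 3.4 calls the six items protocol deviations, and Protocol 3.5.10 bars antimicrobials only up to and during the study. Visit 3 ends the study for a completer, so a drug started later breaches nothing. Sites record medications taken since the previous visit and no later visit is scheduled. The 30-day reporting period concerns adverse events; with five daily doses it ends near Day 35 (5 + 30), only days beyond the Day 22–31 window. The documents do not describe what happens to women who fail, so no value of f is supported. Listing 16.2.3 and the mITT cure rates by arm would expose a large gap between PP and mITT.

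Much of this stands. It narrows the reach mainly to drugs started at Visit 3 itself, plus a few later ones if captured. It does not remove the problem: Visit 3 lies inside the study on any reading, so a limit at study end does not separate drugs started before the exam from those started after it. The listing and the mITT rates reveal the exclusions but do not prevent them.

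A reader might infer something stronger: that PP shrinks towards cured women only and equivalence becomes near automatic. The documents do not support that. It needs f close to 1, and identical products at 36% pass less often at f = 0.75 (82%) than at f = 0 (98.6%).

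**Conclusion.** The gap is real on the text: deviation 1 has no end at the Visit 3 exam, and the exemption misses completers. Followed literally, it selects the primary equivalence population partly on its own endpoint.

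The size depends on f, which is unknown, and on the assumed 200 per arm. With f equal in both arms and up to about 0.5, cure rates are inflated and power falls (94% to 80% at 36% v 40%), while false equivalence stays below 5% in all three margin scenarios. Inflation above 5% needs high f, at a level that depends on the true rates, or more removal in the test arm than in the reference arm. It would therefore be wrong to say that the rule generally favours equivalence.

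This is a should-fix. The stated sample size and the mITT superiority tests are unaffected. The point concerns the analysis population only and takes no view on how women who fail should be managed.

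**What to change.** Before unblinding:

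1. Reword deviation 1 to: *used topical or systemic antimicrobials after randomization and before the Test of Cure (Visit 3) efficacy assessment*. Drugs started at or after that exam then do not exclude.
2. Settle starts dated on the day of Visit 3 from the recorded order or indication, in the blinded pre-lock review that SAP 3.4 already provides for, and document them in the Evaluability Memo.
3. For this rule, do not let the SAP 3.5.6 imputation alone place a partial or missing start date before Visit 3. Decide those cases in the same blinded review.

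Giving deviation 2 the same end point is optional.

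The cost is one reworded SAP sentence, a short note on dates, one condition in the PP program and a few cases in a review already planned. No new data are needed. The small downside is that a few same-day drugs actually taken before the exam may be kept.

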3.5.3.3.1 General

Patients with severe hepatic disease metabolize metronidazole slowly. This results in the accumulation of metronidazole and its metabolites in the plasma. Accordingly, for such patients, metronidazole vaginal gel should be administered cautiously.

Known or previously unrecognized vaginal candidiasis may present more prominent symptoms during therapy with metronidazole vaginal gel. Approximately 6-10% of patients treated with metronidazole vaginal gel developed symptomatic Candida vaginitis during or immediately after therapy.

Disulfiram-like reaction to alcohol has been reported with oral metronidazole, thus the possibility of such a reaction occurring while on metronidazole vaginal gel therapy cannot be excluded.

Metronidazole vaginal gel contains ingredients that may cause burning and irritation of the eye. In the event of accidental contact with the eye, rinse the eye with copious amounts of cool tap water.

3.5.3.3.1.1 Information for the Patient:

The patient should be cautioned about drinking alcohol while being treated with metronidazole vaginal gel. While blood levels are significantly lower with Metronidazole Vaginal Gel than with usual doses of oral metronidazole, a possible interaction with alcohol cannot be excluded.

The patient should be instructed not to engage in vaginal intercourse during treatment with this product (in addition, the protocol requires that the subject not engage in vaginal intercourse for the two days following treatment or for 48 hours prior to Visits 2 and 3).

3.5.3.3.1.2 Drug Interactions

Oral metronidazole has been reported to potentiate the anticoagulant effect of warfarin and other coumarin anticoagulants, resulting in a prolongation of prothrombin time. This possible drug interaction should be considered when metronidazole vaginal gel is prescribed for patients on this type of anticoagulant therapy.

In patients stabilized on relatively high doses of lithium, short-term oral metronidazole therapy has been associated with elevation of serum lithium levels and, in a few cases, signs of lithium toxicity.

Use of cimetidine with oral metronidazole may prolong the half-life and decrease plasma clearance of metronidazole.

3.5.3.3.1.3 Drug/Laboratory Test Interactions

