3.5.10 Prior and Concomitant Medications

Certain medications may interfere with study medication and will not be allowed during the course of the study.

The following may not be used within two weeks of study Entry Visit (Visit 1) or during the study:

- Disulfiram
- Lithium
- Topical or systemic antibiotics
- Topical or systemic antifungals

In addition to the above, the following may not be used at any time during the study:

- Anticoagulation therapy
- Cimetidine
- Any intravaginal products including: Spermicides (including condoms with spermicide lubricants), douches, tampon, feminine deodorant spray, diaphragm, or vaginal ring birth control
- Vaginal therapy
- Any other investigational medication

A subject with recent use of an exclusionary medication may participate if she has discontinued use of the drug for the number of days prior to the screening visit as specified in the

inclusion/exclusion criteria list. The reason for discontinuation of the medication must not be solely for participation in the study. All concomitant treatments will be recorded in the subject's medical records, including the name of the drug, start and stop dates, and reason for use. Other prescriptions for the treatment of intercurrent medical conditions should be discussed with the medical monitor and recorded.

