9.2 Analysis Populations

The following subject populations will be created:

- Intent-to-Treat (ITT) Population: All randomized subjects.
- Safety Population: All subjects who receive at least 1 dose of study drug.
- Modified Intent-to-Treat (mITT) Population: All randomized subjects excluding those who subsequently demonstrate a positive test result for other concomitant vaginal or cervical infections at baseline (e.g. *C trachomatis*, *N. gonorrhoeae*) which may interfere with the efficacy assessment for BV or who have a baseline Nugent score < 4.
- Per Protocol (PP) Population: Includes all subjects who qualify for the mITT population and who follow important components of the trial (including subjects who adhere to treatment and follow-up for efficacy within the prescribed timeframe).

Subjects in the MITT population who discontinue early from the study and do not have an assessment of clinical cure and bacteriological cure will be included in the mITT population analyses as treatment failures. These subjects without outcomes, but are classified as treatment failures will not be included in the PP analyses.

To establish bioequivalence, the 90% confidence interval for the primary endpoint (the difference in the proportion of subjects achieving a clinical cure between metronidazole 0.75% vaginal gel (GDC-229; test product) and metronidazole 0.75% vaginal gel (Oceanside Pharmaceuticals) must be within [0.20, +0.20] for dichotomous variables, using the PP population.

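### PP deviation 1 counts antiseptics, which the protocol does not prohibit outside the vagina, and no planned equivalence interval checks the effect of excluding antifungal users

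*SAP*

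**What the plan says.** SAP 3.4 defines the PP population as "All mITT subjects except for those who had at least one of the protocol deviations listed below". The first listed deviation is that the woman "Used topical or systemic antimicrobial drugs after randomization, this includes the following drug classes: antimycotics, antibacterials, antiprotozoals, gynecological anti-infectives, antiseptics and antifungals". It sets no limit on body site or indication. Deviation 2 separately removes women who used non-study vaginal products.

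There is one exception. "If lack of efficacy (LOE) is the discontinuation reason and the subject took at least 3 doses", she stays in PP as a treatment failure whatever her deviations.

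Protocol 3.5.10 sets the rule that women were asked to follow. Its first list opens "The following may not be used within two weeks of study Entry Visit (Visit 1) or during the study" and names disulfiram, lithium, antibiotics and "Topical or systemic antifungals". A second list, for the study period, adds anticoagulants, cimetidine, intravaginal products, vaginal therapy and other investigational drugs. Antiseptics are in neither list.

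Protocol 9.2 describes the PP set as follows: "Includes all subjects who qualify for the mITT population and who follow important components of the trial". Protocol 3.5.3.3.1, reproducing the marketed gel's label, states: "Approximately 6-10% of patients treated with metronidazole vaginal gel developed symptomatic Candida vaginitis during or immediately after therapy".

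SAP 3.7 and 3.7.1 test equivalence in PP only, and Table 14.2.1 is a PP table. The comparisons with placebo use mITT, where deviation 1 plays no part.

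**The concern.** Two separate matters sit inside one deviation.

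The first is a mismatch between the documents. The SAP treats any antiseptic use as a protocol deviation. A woman who used a skin or mouth antiseptic broke no rule in protocol 3.5.10, yet she leaves the population that decides equivalence. That is hard to square with a PP set meant for women who follow the important parts of the trial.

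The second is informative exclusion. Antifungal use is prohibited, so these women are genuine deviators. But the drug may have been taken for candidiasis that emerged after the gel, which is an event after randomization and possibly related to the product. If the two gels differed in how often this happens, the exclusion would fall unevenly on the arms and could shift the test-minus-reference difference in either direction. The plan has no equivalence interval in which these women are kept, so a reader of the report could not see whether it mattered.

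**Working it through.** **Scope, side by side**

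| Drug used after randomization | Protocol 3.5.10 | SAP deviation 1 | SAP deviation 2 |
|---|---|---|---|
| Non-vaginal antiseptic | not prohibited | excluded | not applicable |
| Vaginal antiseptic | prohibited as intravaginal product or vaginal therapy | excluded | excluded |
| Non-vaginal antifungal | prohibited | excluded | not applicable |
| Vaginal antifungal | prohibited | excluded | excluded |

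Only the first row conflicts. Naming antiseptics adds nobody except non-vaginal users.

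**The plan's own sample size**

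Inputs from protocol 9.1 and SAP 2.5: active cure rate 36%, placebo 20%, test and reference within 4 points, 12.4% lost from mITT, at least 90% power. The continuity-corrected two-proportion formula at two-sided 5% gives 176 per arm. Then 3 × 176 = 528, and 528 / (1 − 0.124) = 603, which is the stated figure. The planned 738 gives 246 × 0.876 = 215.5 mITT women per arm.

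**Removals through antifungal use**

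The documents give a candidiasis rate and no rate of antifungal use. Treating every case as an antifungal user gives an upper bound for this route: 0.06 × 215 = 12.9 and 0.10 × 215 = 21.5, so about 13 to 22 women per active arm.

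**Precision and power**

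The SAP's 90% interval has half-width 1.645 × √(p_T(1 − p_T)/n + p_R(1 − p_R)/n) + 1/n. Power is the normal-approximation probability that both limits lie within ±0.20. Cure rates are 36% and 40%, and PP is assumed to lose nobody for other reasons.

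| Removed per arm | n per arm at N = 738 | Half-width (points) | Equivalence power, N = 738 | Equivalence power, N = 603 |
|---|---|---|---|---|
| 0% | 215.5 | 8.2 | 95.3% | 90.8% |
| 6% | 202.6 | 8.4 | 94.2% | 89.0% |
| 10% | 193.9 | 8.6 | 93.2% | 87.6% |

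The documents give no PP loss rate. If total loss from mITT to PP were 20% (an assumption), power at N = 738 would be 90.2%; at 30% it would be 85.9%.

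**Shift in the difference**

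Assume a true cure rate of 36% in both arms. If a share f is removed and has cure rate q, the PP rate becomes (0.36 − f·q) / (1 − f).

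- Equal f and equal q in both arms: shift 0.
- f = 10% test and 6% reference, all removed women failures: 0.36/0.90 − 0.36/0.94 = 0.400 − 0.383 = +1.7 points.
- Same f, all removed women cured: 0.26/0.90 − 0.30/0.94 = 0.289 − 0.319 = −3.0 points.
- Same f, opposite outcomes in the two arms (the arithmetic extremes): 0.36/0.90 − 0.30/0.94 = +8.1 points, and 0.26/0.90 − 0.36/0.94 = −9.4 points.

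No document supplies the unequal shares or the cure rates among removed women. Antiseptic use is not quantified anywhere, so its effect cannot be sized.

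**The case against.** The strongest reply is that the antifungal part of deviation 1 is the protocol put into practice. Protocol 3.5.10 prohibits topical and systemic antifungals throughout the study, without limit on site or indication, and protocol 9.2 restricts PP to women who follow important components of the trial. This stands. A reader might infer that compliant women are lost on this count too. The documents do not support that; it fits only users of non-vaginal antiseptics.

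A reader might also infer that the gel is expected to cost PP 6-10% of its women. The figure is a rate of symptomatic candidiasis with the marketed gel, not a rate of antifungal use. The label says that patients developed it, which is weaker than saying that the gel causes it.

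A third tempting reading is that the exclusion hides a deficit of the test product. With candidiasis at 15% on test and 6% on reference, and 0-10% cure in affected women against 40% otherwise, the deficit would be (0.15 − 0.06) × (0.40 − 0.10) = 2.7 points up to 0.09 × 0.40 = 3.6 points. But 15% lies outside the reported range and the cure rates are invented. Protocol Table 2 lists the same dose and inactive ingredients for both gels, so similar removal is plausible, though the trial does not guarantee it. The sign can also reverse, as the working shows.

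Finally, other outputs give partial sight of the matter. SAP 3.7.1 presents each arm's mITT cure rate with a 95% CI, SAP 3.3 tabulates deviations by arm, SAP 3.6 tabulates concomitant drug classes by arm, SAP 3.8.2 tabulates adverse events by preferred term, and Listing 16.2.3 lists women excluded from efficacy. This helps, but none of it is a test-minus-reference interval with these women kept. The lack-of-efficacy exception covers discontinued women only: one who attends Visit 3, is scored a failure and used an antifungal still leaves PP. The Evaluability Memo reviews other violations, and nothing in SAP 3.4 lets it restore women removed by deviation 1.

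**Conclusion.** The antiseptic entry is a plain inconsistency between SAP 3.4 and protocol 3.5.10. As written, it can remove protocol-compliant women from the only equivalence population. The number is unknown because the documents give no frequency of antiseptic use.

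The antifungal exclusion agrees with the protocol. What remains is that it can follow from a possibly product-related event after randomization, and that no planned equivalence interval tests its influence. The expected size is small: about 1 to 2 points of power and 0.2 to 0.5 points of half-width at N = 738, with equivalence power alone staying above 90% unless other PP losses are substantial. The shift is zero under equal removal and a few points either way under the assumed 10% against 6%, reaching 8 to 9 points only if removed women have opposite outcomes in the two arms.

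These figures assume that every candidiasis case is treated with an antifungal, cure rates of 36% and 40% for power, and 36% in both arms for the shift. They do not show that the equivalence conclusion is unsafe, and they do not justify rebuilding the primary PP set around users of prohibited drugs. No view is taken on how candidiasis should be treated.

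**What to change.** Before unblinding:

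1. Delete antiseptics from PP deviation 1, or reconcile the entry with protocol 3.5.10 by limiting it to vaginal use.
2. Tabulate deviation 1 exclusions by arm and drug class.
3. Pre-specify a supportive repeat of the Table 14.2.1 90% interval that keeps women whose only PP deviation is antifungal use, with their observed Visit 3 outcome. Include those whose vaginal antifungal is also caught by deviation 2; otherwise the repeat would leave out an unknown share of the women it is meant to examine.
4. Keep the primary PP decision rule as it is, and state that the supportive interval is not a second success criterion.

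The cost is one wording change, one count table and one repeat of an existing table. Protocol 3.5.10 already has the reason for use recorded, and SAP 3.5.6 already codes drug class. The downside is that the supportive table will include users of a prohibited drug, so it should be labelled accordingly.
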